11.4.1. Patient Disposition

The following will be provided:

- The total number of screened patients who have signed the ICF
- The total number of randomized patients that received a randomization number
- The total number of patients who discontinued the study, and the reasons for discontinuation
- A listing of patients treated but not randomized, patients randomized but not treated, and patients randomized but not treated as randomized
- A listing of patients prematurely discontinued from treatment, along with reasons for discontinuation

11.4.2. Demography and Baseline Characteristics

Demographic and baseline characteristics will be summarized descriptively by treatment group, and by all patients combined.

11.4.3. Efficacy Analyses

11.4.3.1. Primary Efficacy Analysis

The co-primary endpoints are the percent change in fasting serum TG from baseline to week 12 and the absolute change in HbA1c from baseline to week 12 between REGN4461 and the placebo arm in cohort A (leptin < 8.0 ng/mL) patients. The glycemic endpoint will be evaluated in the subset of patients with baseline HbA1c > 7.0%. The fasting TG endpoint will be evaluated in the subset of patients with baseline TG > 200 mg/dL. Logarithm transformation will be performed to normalize the fasting TG.

Summary statistics including the mean change (or percent change) from baseline, standard error (SE), corresponding 95% confidence interval, and nominal p-value will be provided by treatment group, using a mixed effect repeated measurement model (MMRM), which will account for the missing data. Nominal p-values will be provided as a measure of the strength of evidence. The model includes the factors (fixed effects) for treatment, week, randomization strata (screening HbA1c \leq 7.0% or HbA1c \geq 7.0%), strata-by-week interaction, and treatment-by-week interaction. Relevant baseline HbA1c, and/or TG will be included as a continuous covariate. Log-transformed TG will be transformed into percentage for presentation.

A non-parametric ranked analysis of covariance (ANCOVA) will be performed for the percent change in fasting serum TG from baseline to week 12 as a sensitivity analysis. The ranked ANCOVA model will be able to provide significance of the treatment effect as compared to placebo. Nominal p-values will be provided as a measure of the strength of evidence. Median treatment difference and 95% confidence interval can be derived from the Hodges-Lehmann estimation and Moses distribution free confidence interval respectively.

For the co-primary endpoints, mean changes $(\pm SE)$ will be plotted over time by the treatment group. A spaghetti plot will be provided for co-primary endpoints by the treatment group. The intra-subject and inter-subject variability may be evaluated if data is appropriate.

11.4.3.2. Secondary Efficacy Analysis

For the secondary analysis, the change from baseline to week 12 will be compared to the change between week 12 and week 24 for study arm 1 to evaluate the treatment effect of REGN4461 on HbA1c and fasting TG.

For continuous secondary endpoints measured in the double-blind period, summary statistics, including the mean (or median) change from baseline, SE, 95% confidence interval, and nominal p-value when appropriate will be provided using the MMRM or ranked ANCOVA (fasting TG only). Descriptive statistics may be provided by subtype of PLD mutations.

For categorical secondary endpoints, appropriate tests, eg,: Fisher's exact test, will be used to evaluate the treatment effect.

In addition to the summary statistics described above, mean changes (\pm SE) will be plotted over time by the treatment group. A spaghetti plot will be provided for co-primary endpoints by the treatment group.

When combining patients from study arm 1 and study arm 2 for determining within-group effects after 12 weeks of REGN4461 treatment, patients in study arm 1 will only be included if they meet

stability criteria for TP1 (when they are receiving placebo). The stability criteria are a change in $HbA1c \le 0.5$ percentage points and a change in $TG \le 25\%$.

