Patients with either moderate abnormalities of both HbA1c (>7.0%) and TG (>200 mg/dL), or a more severe abnormality of TG (>450 mg/dL), with normal or mildly abnormal HbA1c (up to 7.0%) are included. These inclusion criteria are met by the majority of FPLD patients and allow for separate analysis of REGN4461 treatment effects on each metabolic parameter.

The study includes adult patients only. Familial PLD is generally a progressive disease with pubertal onset of fat loss and a long delay between signs/symptoms and diagnosis. As such there is not a large population of pediatric patients with high unmet medical need.

Rationale for Study Endpoints:

The co-primary endpoints are the change in TG from baseline to week 12, and the change in HbA1c from baseline to week 12 in patients in cohort A. These co-primary endpoints were specifically selected because improvements in either or both parameters would help address the highest unmet medical need for PLD patients.

Significant heterogeneity in the response of fasting TG and HbA1c was observed in the metreleptin clinical trials. Given the uncertainty in treatment effect in FPLD patients and the limited number of FPLD patients, secondary endpoints include within-group analyses of all patients receiving their first 12 weeks of REGN4461. This includes individuals in study arm 1 (TP2) and study arm 2 (TP1). In addition, for Study Arm 1, the within group change for TP1 (placebo treatment) will be compared to TP2 (REGN4461 treatment).

The secondary endpoints also include analyses of fasting TG and HbA1c in the higher leptin cohort B. While data from Part B of REGN4461-HV-1794 suggest that a leptin level <8.0 ng/mL might identify individuals most likely to respond, some data suggest response to LEPR agonism in individuals with higher serum leptin, up to 20.0 ng/mL. Analyses of responses in cohort B will therefore allow for more accurate determination of a REGN4461-responsive patient population.

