Placebo run-in period: Enrollment in a clinical trial can significantly affect a patient's diet and adherence to standard-of-care diabetes and hyperlipidemia medications, and thus impact study endpoints. In the initial study of metreleptin, as an example, the effect of study enrollment in improvement of TG was nearly as large as the effect of 1-month of metreleptin therapy (Oral, 2002). For this reason, a 4-week placebo run-in will be used so that any enrollment effect on baseline parameters occurs prior to randomization.

Stratification: A randomized and placebo-controlled study design is chosen to test the efficacy of REGN4461 and control for placebo and study effects on diet. Randomization will be stratified by HbA1c ($\leq 7.0\%$ or $\geq 7.0\%$) within each cohort to ensure that baseline HbA1c is similar between study arms, as not all FPLD patients have high HbA1c.

Treatment Periods: Two treatment periods are included to increase the number of patients who receive active study drug while blinded to treatment allocation, and to increase the power to detect within-group treatment effects and evaluate safety/tolerability. An analysis of REGN4461 treatment effects in patients in study arm 1 (placebo during TP1 and REGN4461 during TP2) is therefore included in secondary endpoints. Note that for endpoints evaluated in this manner, the values at the end of TP1 will serve as the beginning measurement for TP2.

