11.2. Justification of Sample Size

The primary objective is to estimate the treatment effect of REGN4461 on glycemic and lipid parameters. The co-primary endpoints are the percent change in TG and change in HbA1c from baseline to week 12 between the placebo and REGN4461 arms in cohort A.

The size of the study is determined by feasibility assessments. Due to the limited number of identified PLD patients with low leptin and moderate metabolic abnormalities, up to 40 patients will be enrolled.

With a total of 40 patients (20 per cohort, randomized in the ratio of 1:1 into the REGN4461 arm and the placebo arm), the primary analysis will be carried out on the 20 patients in the lower leptin cohort A in TP1. The fact that it is unlikely that all of the patients will have HbA1c >7.0%, ie, not all of the patients will be assessed for the HbA1c endpoint, has also been accounted for. From the feasibility work, it is estimated that 78% of the patients will have elevated baseline HbA1c. With 20 patients in cohort A (10 patients per study arm; Table 3), the half-width of the 90% confidence interval in change from baseline to week 12 between the REGN4461 arm and the placebo arm for HbA1c is 1.4 percentage points, assuming the SD of 1.81%. For TG, the half-width of the 90% confidence interval in logarithm transformed geometric mean ratio (GMR) (REGN4461 week12/baseline divided by placebo week12/baseline) is 0.67, assuming the SD for logarithm transformed fasting TG is 0.87. The SD is estimated from the subset samples of the extracted NIH study data.

Table 3: Half-Width of the 90% Confidence Interval for Primary Endpoints

Endpoint	Number of Patients per Group in the Subset	Half of the 90% confidence interval**
HbA1c*	7	1.72%
HbAIC	8	1.59%
HbA1c [†]	10	1.4%
Fasting TG [†]	10	0.67

^{*}Assuming 78% of the patients have elevated baseline HbA1c.

^{**}The estimate of treatment effects for drug for HbA1c are -1.18%, and -52% for fasting TG. After adjusting for placebo effect, the between-group treatment effect estimate for HbA1c are -0.98%, and -47% for fasting TG. Assuming SD for HbA1c is 1.81%, and logarithm transformed fasting TG is 0.87 (SD of HbA1c and fasting TG is extracted from NIH study data).

[†]Assuming all patients have baseline HbA1c >7.0% and TG >200 mg/dL.

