# 4.7.1. Primary Efficacy Variables

The two primary endpoints of the study are:

- Percent change in fasting serum TG from baseline to week 12.
- Absolute change in HbA1c from baseline to week 12.

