## 5.7.2. Analysis of Secondary Efficacy Variables

Statistical analyses for the secondary efficacy endpoints (defined in Section 4.7.2) and SBTP-specific secondary efficacy endpoints (described in Section 4.7.3) will be performed in the FAS population.

All measurements, scheduled or unscheduled, will be assigned to efficacy analysis windows defined in Appendix 10.2 in order to provide an assessment for these time points. For fasting TG, measurements on not-fasting patients will be excluded; the median percent changes (with Q1 and Q3 bars) will be plotted across visits by treatment group.

Multiple types of measurements are planned to be analyzed during differing time points in the trial, specifically continuous measurements expected to have a normal distribution (example: absolute change in HbA1c) and continuous measurements expected to have a non-normal distribution (example: TG).

The following patient groups are also used for analyzing secondary efficacy variables:

- Combined Cohort A+B include all patients in Cohort A and Cohort B as defined in Section 2.1.
- DBTP-stable patient is defined as a patient who meets both of the following two stability criteria:
  - Absolute change in HbA1c from baseline to week  $12 \le 0.5\%$
  - Percent change in fasting serum TG from baseline to week  $12 \le 25\%$

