# Table 5. Summary of Descriptive Statistics in Normally Distributed Secondary Endpoints based on REGN4461 Exposure

NOTE: Efficacy data for study treatment arm 1 (placebo) and arm 2 (REGN4461) will be combined by re-aligning to the first REGN4461 treatment administration, specifically study day 1 for arm 2 and week 12 for arm 1 will become REGN4461 Day 1. These descriptive statistics will be presented three times, specifically in Cohort A, Cohort B, and Cohort A+B.

Endpoints	Descriptive Statistic	
Absolute change in HbA1c from baseline to week 12	HbA1c mean changes from REGN4461     Day 1 to REGN4461 week 12 for combined DBTP-stable Arm 1 patients and Arm 2 patients will be provided along	

Regeneron Pharmaceuticals, Inc.

Page 38 of 88

Protocol: R4461-PLD-20100

• Absolute change in HbA1c from week 12 to week 24	with its corresponding 95% confidence interval.

 
Change in fasting glucose from baseline to week 12
 
Change in fasting glucose from week 12 to week 24
 
	• Fasting glucose mean changes from REGN4461 Day 1 to REGN4461 week 12 for combined Arm 1 and Arm 2 patients will be provided along with its corresponding 95% confidence interval.

 
Percent change in liver fat (MRI-PDFF) from baseline to week 12
 
Percent change in liver fat (MRI-PDFF) from week 12 to week 24
 
	• Liver fat (MRI-PDFF) mean changes from REGN4461 Day 1 to REGN4461 week 12 for combined Arm 1 and Arm 2 in patients with hepatic steatosis (baseline MRI-PDFF ≥8.5%) will be provided along with its corresponding 95% confidence interval.

Table 6. Summary of Statistics for Patients Randomized to Placebo in Normally distributed Secondary Endpoints

NOTE: These statistical estimates and descriptive statistics will be presented three times, specifically in Cohort A, Cohort B, and Cohort A+B.

Endpoints	Estimates	Comparison

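### On the planning SDs, the placebo-stability rule for the pooled first-12-weeks HbA1c and TG results removes most of Arm 1, and it does not state whether its limits are two-sided

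*Protocol*

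**What the plan says.** Protocol 3.2.1 explains that FPLD patients are few and responses uncertain, so "secondary endpoints include within-group analyses of all patients receiving their first 12 weeks of REGN4461", meaning Arm 1 in TP2 and Arm 2 in TP1. The same section says that two treatment periods are used, among other reasons, "to increase the power to detect within-group treatment effects".

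Protocol 4.2 and 11.4.3.2 then restrict the pool. When the arms are combined, "patients in study arm 1 will only be included if they meet" the stability criteria in TP1, while on placebo. The rule reads: "The stability criteria are a change in $HbA1c \le 0.5$ percentage points and a change in $TG \le 25" per cent. Section 4.2 attaches it to the pooled TG and HbA1c endpoints and not to pooled fasting glucose or liver fat.

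SAP 5.7.2 makes the condition joint: "DBTP-stable patient is defined as a patient who meets both of the following two stability criteria". The SAP tables differ in how they apply it:

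- Table 5, pooled HbA1c: stable Arm 1 patients plus Arm 2.
- Table 5, pooled glucose: "Fasting glucose mean changes from REGN4461 Day 1 to REGN4461 week 12 for combined Arm 1 and Arm 2 patients", with no stability condition. Liver fat is handled the same way.
- Table 7, pooled TG: combined Arm 1 and Arm 2, without naming the filter that protocol 4.2 requires. The text before the table does mention refitting the model without unstable Arm 1 patients.

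Neither document estimates how many Arm 1 patients will pass.

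**The concern.** The pooled endpoints exist to make use of scarce patients. A filter that most placebo patients fail through ordinary variability works against that purpose and against the all-patients description in 3.2.1.

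Three further features matter. The filter selects Arm 1 patients on a post-randomisation outcome, while Arm 2 enters unselected. Because both limits apply to each endpoint, a TG swing removes a patient from the HbA1c result and the reverse; no reason is given. And the limits carry no modulus or plus-minus sign. The SAP's word absolute does not settle this, because "Absolute change in HbA1c from baseline to week 12" is also its name for the signed primary endpoint.

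At stake are the precision and the meaning of two secondary results. The primary comparison is not affected.

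**Working it through.** **Inputs.** Protocol 11.2 and Table 3: HbA1c SD 1.81, log TG SD 0.87, drug-arm effects -1.18 points and -52%, placebo-adjusted effects -0.98 points and -47%. Protocol 6.1.1: 10 Arm 1 patients per cohort.

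**Reproducing the plan's figure.** Half-width of the 90% CI = t(0.95, 2n-2) × SD × sqrt(2/n).

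| Endpoint | n per arm | Computed | Table 3 |
|---|---|---|---|
| HbA1c | 7 | 1.724 | 1.72 |
| HbA1c | 8 | 1.594 | 1.59 |
| HbA1c | 10 | 1.404 | 1.4 |
| log TG | 10 | 0.675 | 0.67 |

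The plan states that the half-width "for HbA1c is 1.4 percentage points, assuming the SD of 1.81" per cent, and the match shows that 1.81 and 0.87 are used as SDs of change from baseline.

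**Placebo means.** Either zero, or those implied by the plan: HbA1c -1.18 + 0.98 = -0.20; log TG ln(0.48/0.53) = -0.099.

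**Limits.** HbA1c 0.5 points; log TG ln(1.25) = 0.223, with ln(0.75) = -0.288 as the lower limit if two-sided. Changes are taken as normal on these scales.

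**Two-sided reading, independent changes.**
- Zero means: 0.218 × 0.231 = 0.050.
- Implied placebo means: 0.216 × 0.230 = 0.050.
- Correlation 0.5 gives 0.057; 0.7 gives 0.068; 0.9 gives 0.103.
- Expected yield at 0.05: 0.5 of 10 per cohort; chance of none 0.95^10 = 0.60.
- Both SDs halved: 0.18-0.19 at correlation 0, and 0.20-0.21 at 0.5.
- If the 22% of patients with HbA1c ≤7.0% always met the HbA1c limit: (0.22 + 0.78 × 0.22) × 0.23 = 0.09, or 0.9 of 10.

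**As written, upper bounds only.**
- Zero means: 0.609 × 0.601 = 0.37.
- Implied placebo means: 0.651 × 0.645 = 0.42.
- Correlation 0.5 gives 0.44 to 0.49; 0.7 gives 0.48 to 0.53.
- Both SDs halved, independent: 0.710 × 0.696 = 0.49 with zero means; 0.780 × 0.771 = 0.60 with the implied means.

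**Who is kept under the upper-bound reading.** The mean of a normal variable below a limit u is m - s × φ(x)/Φ(x), with x = (u - m)/s.
- HbA1c, zero mean: -1.81 × 0.384/0.609 = -1.14. Implied mean: -0.20 - 1.81 × 0.370/0.651 = -1.23.
- log TG, zero mean: -0.87 × 0.386/0.601 = -0.559, a geometric mean 43% lower. Implied mean: -0.099 - 0.87 × 0.373/0.645 = -0.602, 45% lower.
- At correlation 0.5, by simulation: HbA1c -1.31 to -1.39 and TG 47-49% lower.

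**Precision of the pooled HbA1c change, SE = 1.81/sqrt(n).** All 20 patients of a cohort: 0.40. Two-sided filter, about 10.5 patients: 0.56, about 38% wider. Upper bounds only, about 14 patients: 0.48, about 20% wider.

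**The case against.** A reader might infer that the pooled analysis is in effect Arm 2 alone. The documents do not support that as a general statement. The 5% needs a lower limit that neither document writes; as written, about 4 of 10 Arm 1 patients stay. It also needs HbA1c and TG changes that are at most moderately correlated. Pooled glucose and liver fat use all of Arm 1, and the pooled TG row of SAP Table 7 does not name the filter. Arm 1 data on drug are also used without the filter in the within-arm comparison of TP2 with TP1.

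The SDs are open to challenge. They come from NIH study data (the SAP cites a metreleptin-response study), and 0.87 is worded as the SD of log TG rather than of its change. Placebo patients on stable medication, after a 4-week run-in, may vary less. Protocol 6.1 also averages weeks 10 to 12 for the end-of-TP1 value. This stands: the shares are illustrative, and with halved SDs the upper-bound reading keeps about half or more.

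A rule about stability on placebo can apply only to Arm 1, and excluding patients whose starting value is drifting is a recognisable choice. Section 3.2.1 is rationale text, whereas the endpoint section states the filter openly. Both points are fair. They do not explain why both criteria apply to each endpoint or why glucose and HbA1c differ, and the upper-bound reading does not select stable patients.

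Finally, SAP 1.2.4 limits efficacy to descriptive summaries and plots after early termination. That lowers the stakes and makes the 10-per-arm counts a statement about the design as planned. The pooled HbA1c summary was already descriptive, and losing patients costs relatively more when fewer are enrolled.

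**Conclusion.** The point holds for the pooled HbA1c and TG endpoints only. On the planning SDs, with normal changes and correlation between 0 and 0.5, either reading removes more than half of Arm 1. The two-sided reading keeps about 5-6%, or about 18-21% with both SDs halved. The upper-bound reading keeps about 37-49%, and those kept had fallen on average by about 1.1 to 1.4 HbA1c points, with geometric mean TG about 43-49% lower. Part of such a fall would tend to reverse after week 12 by regression to the mean, which would obscure the change on drug.

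The more-than-half statement has limits: under the upper-bound reading it can fail at correlation 0.7 or with halved SDs. No placebo SD is available to narrow the range. What remains in any case is a rule with no stated direction, no expected yield, selection on a post-randomisation outcome in one arm, and uneven application across SAP Tables 5 and 7. This is a worthwhile improvement of modest priority.

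**What to change.** In SAP Tables 5 and 7, report the pooled first-12-week HbA1c and TG changes for all Arm 1 plus Arm 2 patients, in line with protocol 3.2.1, and label them as uncontrolled within-group changes. Show the DBTP-stable subset as a separate row with the number of Arm 1 patients retained. For that subset, write the limits as two-sided (the modulus of the change) and apply only the criterion of the endpoint being summarised: HbA1c for HbA1c, TG for TG. State in the TG row of Table 7 which set each line uses.

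The cost is SAP wording and a few table rows, with no new data. The downside is that the unfiltered pool includes Arm 1 patients whose starting value drifted on placebo. The uncontrolled label and the adjacent stable-subset row make that visible.

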11.4.4. Control of Multiplicity

Not applicable.

11.4.5. Safety Analysis

11.4.5.1. Adverse Events

Definitions

For safety variables, 3 observation periods are defined:

- The pretreatment period is defined as the time from signing the ICF to before the first dose of study drug.
- The on-treatment period is defined as the day from first dose of study drug to the last dose of study drug plus 7 days.
- The posttreatment period is defined as the end of the on-treatment period to the last study visit.

Treatment-emergent adverse events (TEAEs) are defined as those that are not present at baseline or represent the exacerbation of a pre-existing condition during the on-treatment period.

TEAEs will be summarized for each of the following periods: double-blind treatment period, single-blind treatment period, follow-up period, and combined across the treatment periods and follow-up period. Adverse events that occur prior to treatment period 1 (day 1) will be listed.

Analysis

All AEs will be coded using the Medical Dictionary for Regulatory Activities (MedDRA®). Summaries of all TEAEs by treatment group will include:

- Overview of TEAEs, ie, overall number (%) of patients with any TEAE, related TEAEs, serious TEAE, TEAEs leading to death, TEAEs leading to study discontinuation, or AESIs
- All TEAEs by primary SOC and PT
- TEAEs by severity (according to the grading scale outlined in Section 10.3.1), presented by SOC and PT
- TEAEs by causality relationship to treatment (related, not related), presented by SOC and PT
- Treatment-emergent SAEs by primary SOC and PT
- Treatment-emergent AESIs
- Treatment-emergent AEs leading to discontinuation by primary SOC and PT
- Treatment-emergent SAEs leading to death, by primary SOC and PT

Deaths and other SAEs will be summarized by treatment group.

Treatment-emergent adverse events leading to permanent treatment discontinuation will be summarized by treatment group.

11.4.5.2. Other Safety

Vital Signs

Vital signs (temperature, pulse, blood pressure, and respiration rate) will be summarized by baseline and change from baseline to each scheduled assessment time with descriptive statistics.

Laboratory Tests

Laboratory test results will be summarized by baseline and change from baseline to each scheduled assessment time with descriptive statistics.

Number and percentage of patients with a potentially clinically significant value (PCSV) at any post-randomization time point will be summarized for each clinical laboratory test for all patients and separately for patients in whom the PCSV criterion was normal or missing at baseline.

Shift tables based on baseline normal/abnormal and other tabular and graphical methods may be used to present the results for laboratory tests of interest.

